1 PROTOCOL SUMMARY

1.1 Synopsis

Protocol Title: A Study to Assess the Effect of Single Doses of MK -5475 on Pulmonary Vascular Resistance in Patients with Moderate to Severe Pulmonary Arterial Hypertension

Short Title: Dosing of MK-5475 in Participants with Pulmonary Hypertension

Acronym: N/A

Hypotheses, Objectives, and Endpoints:

Hypotheses are aligned with objectives in the Objectives and Endpoints table.

This study is to be conducted in male and female participants with group 1 pulmonary arterial hypertension (PAH).

Primary Objectives	Primary Endpoints
- To evaluate the safety and tolerability of MK-5475 in participants with pulmonary arterial hypertension (PAH). (All parts)	Safety and tolerability will be evaluated during clinical assessments that include vital signs, safety laboratory testing, physical examinations, ECG readings, PFTs and review of adverse events.
- To assess the duration and effect following a single inhaled dose of MK-5475 on pulmonary vascular resistance (PVR) in participants with pulmonary arterial hypertension (PAH). (Part 2, Period 2 (Panel A) and Period 3 (Panels B, C and D))	Peak reduction from baseline in PVR after a single inhaled dose of MK-5475
Secondary Objectives	Secondary Endpoints
- To estimate the effect of MK-5475 given as single inhaled doses on systemic hemodynamic parameters (heart rate (HR), systolic and diastolic blood pressure (BP)) in participants with pulmonary arterial hypertension. (Part 2 Period 2 (Panel A) and Period 3 (Panels B, C and D))	- HR and BP change from baseline at 0.5, 4.5, and 24 (or prior to discharge) hours post-dose.
- To assess the effect following a single inhaled dose of MK-5475 on pulmonary blood volume (PBV) in participants with pulmonary arterial hypertension. (Part 2, Period 3 (Panel A) and Period 2 (Panels B, C and D))	- Increases from baseline PBV at 1, 3, 8 and 24 hours postdose.

Overall Design:

Study Phase	Phase 1
Primary Purpose	Treatment
Indication	Pulmonary Arterial Hypertension (PAH)
Population	Participants with moderate to severe Group 1 PAH
Study Type	Interventional
Intervention Model	Sequential This is a single-site study.
Type of Control	Not applicable
Study Blinding	Double-blind
Masking	Data Analyst
Estimated Duration of Study	The Sponsor estimates that the study will require approximately 22 months from the time the first participant signs the informed consent until the last participant's last study-related telephone call or visit.

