3 HYPOTHESES, OBJECTIVES, AND ENDPOINTS

Hypotheses are aligned with objectives in the Objectives and Endpoints table.

This study is to be conducted in male and female participants with group 1 pulmonary arterial hypertension (PAH).

Objectives	Endpoints
Primary	

 To evaluate the safety and tolerability of MK-5475 in participants with pulmonary arterial hypertension (PAH). (All parts) 	Safety and tolerability will be evaluated during clinical assessments that include vital signs, safety laboratory testing, physical examinations, ECG readings, PFTs and review of adverse events.

 To assess the duration and effect following a single inhaled dose of MK-5475 on pulmonary vascular resistance (PVR) in participants with pulmonary arterial hypertension (PAH). (Part 2, Period 2 (Panel A) and Period 3 (Panels B, C and D)) 	Peak reduction from baseline in PVR after a single inhaled dose of MK-5475
Secondary	

 To estimate the effect of MK-5475 given as single inhaled doses on systemic hemodynamic parameters (heart rate (HR), systolic and diastolic blood pressure (BP)) in participants with pulmonary arterial hypertension. (Part 2 Period 2 (Panel A) and Period 3 (Panels B, C and D)) 	
 HR and BP change from baseline at 0.5, 4.5, and 24 (or prior to discharge) hours post-dose.

 To obtain preliminary plasma pharmacokinetic (PK) data of MK-5475 (e.g. area under the curve (AUC) 0-24, AUC 0-∞, C_{max}, C₂₄, T_{max}, t_{1/2}) in participants with pulmonary arterial hypertension. (Part 1 and 2) 	
 AUC 0-∞, AUC 0-24, C_{max}, C₂₄, T_{max}, apparent terminal half-life

 To assess the effect following a single inhaled dose of MK-5475 on pulmonary blood volume (PBV) in participants with pulmonary arterial hypertension. (Part 2, Period 3 (Panel A) and Period 2 (Panels B, C and D)) 	
 Increases from baseline PBV at 1, 3, 8 and 24 hours postdose.

Objectives	Endpoints
Tertiary/Exploratory	

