9.1 Statistical Analysis Plan Summary

Statistical Methods

Primary Objective (PVR): For the primary pharmacodynamic parameter PVR, the peak percent reduction compared to baseline in PVR after a single inhaled dose of MK-5475 will be analyzed for Part 2, the RHC period. The difference from baseline will be assessed on the log scale and then back-transformed for reporting (percent change from baseline).

Primary Objective (Safety): Incidence of AEs will be descriptively summarized. Summary statistics and plots will be generated for the change from baseline values in the VS, ECG parameters, and selected laboratory safety parameters for participants, as deemed clinically appropriate. Depending on the safety parameter, the difference from baseline will either be computed on the original scale (raw change from baseline) or on the log scale and back-transformed for reporting (percent change from baseline). Summary statistics for the raw laboratory safety tests, ECGs, and/or VS may also be computed, as deemed clinically appropriate.

Secondary Objective (HR, BP, and PBV): The predose baseline values for HR and BP will be obtained as outlined in Section 8.3.2.1. The mean change from baseline for the HR and BP will be calculated at 0.5, 4.5, and 24 hours post-dose for Part 2, Period 2 or 3 only.

PBV will be measured using CT scans with an IV iodinated contrast agent before and after administration of MK-5475. An increase from baseline in measured PBV would be calculated at 1, 3 and 8 hours for Part 2, the FRI period only.

Secondary Objective (PK): Separately for each PK parameter (Panel A, Part 1, Periods 1, 2 and 3, and Panels B-D, Part 2, Period 1), individual values of AUC_{0-24hr} , $AUC_{0-\infty}$, C_{max} , C_{24} , at each dose level will be natural log-transformed and evaluated with a linear mixed effects model containing a fixed effect for treatment, and Panel a random effect for participant. Kenward and Roger's method will be used to calculate the denominator degrees of freedom for the fixed effects. Ninety-five percent confidence intervals for the least squares means for each treatment will be constructed on the natural log scale and will reference a t-distribution. Exponentiating the least-squares means and lower and upper limits of these confidence intervals will yield estimates for the population geometric means and confidence intervals about the geometric means on the original scale.

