9.3 Hypotheses/Estimation

Primary Objectives:

- To evaluate the safety and tolerability of MK-5475 in participants with pulmonary arterial hypertension (PAH).
- To assess the duration and effect following a single inhaled dose of MK-5475 on pulmonary vascular resistance (PVR) in participants with pulmonary arterial hypertension (PAH).

Secondary Objectives:

- To estimate the effect of MK-5475 given as single inhaled doses on systemic hemodynamic parameters (heart rate (HR), systolic and diastolic blood pressure (BP)) in participants with pulmonary arterial hypertension.
- To obtain preliminary plasma pharmacokinetic (PK) data of MK-5475 (e.g. area under the curve (AUC) 0-24, AUC 0-∞, C_{max}, C₂₄, T_{max}, t_{1/2}) in participants with pulmonary arterial hypertension.
- To assess the effect following a single inhaled dose of MK-5475 on pulmonary blood volume (PBV) in participants with pulmonary arterial hypertension.

Exploratory Objectives:

- To explore the relationship of MK-5475 concentration and summarize changes in pulmonary vascular resistance, pulmonary arterial pressure, cardiac output/cardiac index (CO/CI), systemic vascular resistance, mixed venous oxygen saturation and arterial oxygenation in participants with pulmonary arterial hypertension.
- To explore the effect of single doses of MK-5475 on the ratio of change from baseline in pulmonary vascular resistance / change from baseline in systemic vascular resistance.
- •To explore the relationship between mean change differences in pulmonary vascular resistance (PVR) and baseline changes in pulmonary blood volume (PBV) following a single dose of MK-5475.

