9.6 Statistical Methods

Primary (PVR): Fold change from baseline individual PVR in Part 2, RHC Period only will be calculated for each postdose time point. The largest reduction from baseline will be identified for each participant. These reductions will be natural log-transformed and mean and 95% confidence interval calculated based on a t-distribution at each dose-level. These will be exponentiated and expressed as percents to obtain the geometric mean and 95% CI for percent reduction in PVR.

Primary (Safety): Incidence of AEs will be descriptively summarized. Summary statistics and plots will be generated for the change from baseline values in the VS, ECG parameters, and selected laboratory safety parameters for participants, as deemed clinically appropriate. Depending on the safety parameter, the difference from baseline will either be computed on the original scale (raw change from baseline) or on the log scale and back-transformed for reporting (percent change from baseline). Summary statistics for the raw laboratory safety tests, ECGs, and/or VS may also be computed, as deemed clinically appropriate.

Secondary (HR and BP): Each of these parameters will be analyzed separately for Part 2, RHC period only. Individual PD parameters (HR, SBP, and DBP) will be natural log transformed and analyzed in a linear mixed effects model with fixed effects for dose, time (0.5, 4.5, and 24 hours), dose by time interaction and a random effect for participant. The dependent variable is: PD_postdose – PD_predose (PD=HR, SBP, DBP). An unstructured covariance matrix for each time point will be used to allow for unequal variances via the REPEATED statement in SAS PROC MIXED (a similar model would be acceptable using R) Kenward and Roger's method will be used to calculate the denominator degrees of freedom for the fixed effects (DDFM=KR). If the model fails to converge, a simpler covariance structure such as compound symmetry may be used. The difference in least squares means with 95% CI will be calculated for post dose of MK-5475 versus predose of MK-5475 at each dose level by time.

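### The primary PVR figure averages individual peaks: read as drug effect it is biased toward a reduction, and nothing at primary level measures duration

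*Combined protocol and SAP*

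**What the plan says.** The primary pharmacodynamic objective (Section 3, repeated in 9.3) is "To assess the duration and effect following a single inhaled dose of MK-5475 on pulmonary vascular resistance (PVR". The only primary PVR endpoint, in the synopsis and Section 3, is "Peak reduction from baseline in PVR after a single inhaled dose of MK-5475".

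Section 9.6 gives the analysis in three steps:
- Each person's PVR at every reading after dosing in the RHC period is divided by that person's baseline.
- One value per person is then kept: "The largest reduction from baseline will be identified for each participant".
- Only the kept values are summarized, and this is where the interval comes in: "These reductions will be natural log-transformed and mean and 95% confidence interval calculated based on a t-distribution at each dose-level".

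Section 9.1 also analyses only the peak and adds "The difference from baseline will be assessed on the log scale and then back-transformed for reporting (percent change from baseline". The RHC table in Section 1.3 schedules six post-dose readings, at 0.5, 1, 2, 3, 4 and 4.5 h. Part 2 is open label (6.3.3); placebo dosing belongs to Part 1 and to inhaler training.

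Beyond the intermediate fold change, PVR over time appears only at exploratory level. Section 9.3 has an objective "To explore the relationship of MK-5475 concentration and summarize changes in pulmonary vascular resistance" and other haemodynamic variables. Section 9.4 lists PVR change at 1 and 3 h, and PVR/SVR change from 0.5 through 4.5 h. Section 9.6 plans graphs with optional modelling. None of these states a CI. For HR and BP, by contrast, 9.6 specifies a model with an estimate for every dose and time: "The difference in least squares means with 95% CI will be calculated for post dose of MK-5475 versus predose of MK-5475". PBV also has a by-time model.

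**The concern.** The lowest of six noisy ratios is below 1 on average even if PVR does not change. Averaging over participants does not remove this, and a larger n only tightens the interval around the shifted value. With no placebo catheterization there is nothing to subtract. A reader who sets the reported CI against zero would therefore take selection of the lowest reading for a fall in PVR.

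This matters most where the true effect may be small. Section 4.2 adds 120 µg in Panel D to study the lower end of the PK/PD relationship. At an assumed log-SD of 0.10, an inactive dose compared with a waning effect of 20% at its maximum (a true gap of 20 points) would show a gap of only about 12 to 14 points on the peak scale.

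A peak also says nothing about how long an effect lasts. With no duration measure defined, any statement on that half of the objective would be chosen after the data are seen.

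**Working it through.** **The plan's own figure.** There is none to reproduce. Section 9.9 gives a sample size of twenty without SD, effect, alpha or power, and says that no variability estimates exist.

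**Inputs from the documents.** Six post-dose readings (1.3). Baseline is the mean of the last two readings; two consecutive values must agree within 15%, with up to four attempts (4.1). Participants per dose in the RHC period, from Table 1 and 4.1: up to 7 at 120 µg, 8 at 240 µg, and 4 + 8 = 12 at 360 µg.

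**Assumptions.** Log-normal readings with within-participant log-SD σ of 0.05 to 0.15. Post-dose errors are independent, equally correlated at 0.5, or autocorrelated at 0.8 per hour. At σ = 0.15 the 15% rule rejects 44% of first pairs and 11% of participants, so the top of the range is less plausible.

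**No drug effect, closed form.** The expected maximum of six standard normals is 1.267, so the expected peak log ratio is −1.267 × σ × √(1 − ρ).
- σ = 0.10, ρ = 0: 1 − exp(−0.1267) = 11.9%.
- σ = 0.10, ρ = 0.5: 1 − exp(−0.1267 × 0.707) = 8.6%.

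**No drug effect, simulation with the baseline rule.** Apparent peak reduction (%):

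| log-SD | independent | correlation 0.5 | autocorrelation 0.8 |
|---|---|---|---|
| 0.05 | 6.2 | 4.4 | 3.4 |
| 0.08 | 9.7 | 7.0 | 5.5 |
| 0.10 | 12.0 | 8.6 | 6.8 |
| 0.15 | 17.4 | 12.6 | 10.0 |

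Share of trials whose peak CI lies wholly on the reduction side, at σ = 0.10:

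| n | independent | correlation 0.5 | autocorrelation 0.8 |
|---|---|---|---|
| 7 | 82% | 43% | 27% |
| 12 | 99% | 72% | 48% |

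For the CI at one fixed time the share is about 2.5%. At least one of six by-time CIs does so in about 7 to 13%.

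**True mean curve with a 20% maximum, the same for everyone.** Over the SD and correlation range, the peak reports 20 to 29% for a waning curve (12, 20, 16, 11, 7, 5% at the six times) and 22 to 32% for a plateau (12, 20, 20, 20, 18, 16%). By-time geometric means are off by less than 0.2 points.

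**Duration.** The peak ranges for these two curves overlap heavily, although the true reductions at 4.5 h are 5% and 16%. A time-averaged log ratio separates them. Trapezoid weights over the 4 h from 0.5 to 4.5 h are 0.0625, 0.1875, 0.25, 0.25, 0.1875 and 0.0625.
- Waning: 0.0625 ln 0.88 + 0.1875 ln 0.80 + 0.25 ln 0.84 + 0.25 ln 0.89 + 0.1875 ln 0.93 + 0.0625 ln 0.95 = −0.139, an average reduction of 13.0%.
- Plateau, same weights on 0.88, 0.80, 0.80, 0.80, 0.82, 0.84: −0.210, or 18.9%.

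**Precision of a by-time estimate.** At σ = 0.10 with independent errors, the SD of the log ratio is 0.10 × √(1 + 1/2) = 0.1225. At n = 7 the half-width is 2.447 × 0.1225/√7 = 0.113, or about −11% to +12% around the estimate.

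**Covariance parameters.** Six times need 6 × 7/2 = 21 for one common matrix. A separate matrix for each of three doses would need 63.

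**The case against.** The strongest reply is that the method does what it declares. The endpoint is peak reduction and 9.6 estimates its mean. Section 9.8 says there are no hypotheses, 4.2.1.1 says there are no efficacy endpoints, and nowhere does the plan compare the peak CI with zero. This stands. A reader might infer a type I error breach, but with no test there is no error rate to breach. The problem is one of bias and interpretation.

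A second reply is that individuals may truly reach their lowest PVR at different times. Section 2.2.3 reports moderate to high variability in exposure within and between participants. In a noise-free illustration with four equal groups, each with a true 20% nadir at 0.5, 1, 2 or 3 h, the individual peak is correctly 20.0% while the largest by-time mean is 14.8%. This also stands: a reader might treat all of the gap between peak and by-time means as noise, and the documents do not support that.

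Third, PVR over time is not ignored, as the exploratory list shows. The gap is narrower: no by-time PVR estimate with a CI at primary level, and no duration measure.

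Fourth, a duration rule built on significance would bring its own fault. For the waning curve at σ = 0.10 with independent errors, an unbroken run of CIs below no change, starting at 1 h, reaches at least 3 h in 49% of trials at n = 7 but 84% at n = 12. Identical effects would then tend to look longer at 360 µg than at 120 µg. The fix avoids such a rule.

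Finally, the study is ongoing and Part 2 is open label, so naming a time now is only partly prespecification.

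**Conclusion.** The concern holds in this limited form. The peak summary is valid for the declared endpoint. As a measure of drug effect it is biased toward a reduction, with certain direction whenever readings vary within participants. The size rests on the assumed SD and correlation: with no effect, about 3 to 17% apparent reduction over log-SD 0.05 to 0.15. At SD 0.10 the peak CI lies wholly on the reduction side in 27 to 82% of trials at n = 7 and 48 to 99% at n = 12. The blinded waveform reading in 8.7.1 does not remove this, because the selection comes after the readings.

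The duration half of the primary objective has no specified estimate, and that needs no assumption. Drift common to all participants, and regression to the mean from the baseline PVR entry threshold in 4.1, are outside these figures.

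**What to change.** 1. Keep peak reduction as the declared endpoint, label it descriptive, and state that its CI is not to be compared with zero.
2. Add to the primary PVR analysis a repeated-measures model of ln(PVR at t / baseline PVR) with dose, time and dose-by-time over 0.5 to 4.5 h. Use one covariance matrix common to all doses (21 parameters), with compound symmetry as fallback. Report the geometric mean ratio and pointwise 95% CI at each time and dose.
3. Address duration with this profile to 4.5 h and a summary that does not depend on CI significance, for example the time-averaged log ratio over 0.5 to 4.5 h and the estimated ratio at 4.5 h, each with its CI. Do not define duration as a run of significant CIs.
4. If one time is chosen for the main effect statement, give the reason, and disclose in the CSR (under 9.2) when it was chosen relative to PVR data already seen.
5. State that drift common to all participants remains uncontrolled.
6. Reword 9.6 so that the fold change, not the reduction, is what is logged, as 9.1 implies.

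The cost is one added model on data already collected, plus SAP text. No procedure, participant or declared endpoint changes. The downsides are a smaller headline figure than the peak, and by-time means that can understate individual peak response when nadir times differ.

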2.2.3 Ongoing Clinical Studies

PN002: Dosing of MK-5475 in Participants with Pulmonary Hypertension (Current Study)

In this 2-part study evaluating the safety, PK and PD [right heart catheterization (RHC) and functional respiratory imaging (FRI)], single-dose MK-5475 ranging from 120 to 360 µg in participants with moderate to severe group 1 PAH is generally well-tolerated. To date, no serious adverse events (SAEs) were reported and no participants discontinued due to an AE. Adverse events (AEs) were mild to moderate in intensity. A total of 45 AEs in 15 of 18 participants were reported. Of these, 9 AEs were considered related to study drug by the investigator. AEs deemed related were rhinitis (1), dizziness (1), ALT increased (2.94 x ULN) (1) bilirubin increased (1.18 and 2.13 x ULN)(2) hyperkalemia (1.02 to 1.07 xULN) (3) and platelet count decreased (0.33 below LLN) (1). Refer to the Investigator's Brochure for a full listing of AEs to date.

Following single inhaled MK-5475 administration, moderate to high inter- and intra-individual variability in AUC and C_{max} was observed in PAH participants compared to healthy participants. Geometric mean AUC₀₋₂₄ in PAH participants ranged from 0.259 to 4.28 nM*hr for the 120 to 360 µg dose levels across study panels/periods. Geometric mean AUC₀₋₂₄ in PAH participants at 240 µg ranged from 1.04 to 1.71 nM*hr. Geometric mean AUC₀₋₂₄ in PAH participants at the 300 µg dose level ranged from 2.08 to 2.35 nM*hr across study panels, The geometric mean AUC₀₋₂₄ at the 360 µg dose level in PAH participants ranged 1.21 to 4.28 nM*hr. Geometric mean AUC₀₋₂₄ in all study populations thus far has remained below the AUC₀₋₂₄ corresponding to NOAEL in 1 month tox study in dogs (4.5 nM*hr). A total of four PAH participants reached an AUC₀₋₂₄ higher than the dog NOAEL exposure in at least one of the periods in the study: one dosed at 300 µg (7.25 nM*hr) and three dosed at 360 µg (4.53 to 6.99 nM*hr). The highest individual AUC₀₋₂₄ at the 360 µg dose level in PAH participants was 6.99 nM*hr which is about 1.6-fold above the NOAEL. Although this was above the 1-month dog NOAEL, the total dose delivered remained below the NOAEL dose of 500 µg. Safety and tolerability profile in participants in whom individual AUC₀₋₂₄ levels exceeded the NOAEL AUC₀₋₂₄ appears similar to other participants.

PN004: MK5475 Sildenafil DDI Study

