6.3 Measures to Minimize Bias: Randomization and Blinding

6.3.1 Intervention Assignment

Participants will be assigned randomly according to a computer-generated allocation schedule. A sample allocation schedule is provided in [Table 3](#) below.

Table 3 Sample Allocation Schedule

Panel A ^a					
Participant (N)	Part 1 Period 1	Part 1 Period 2	Part 1 Period 3	Part 2 Period 2	Part 2 Period 3
N=2	120µg	Placebo	240 µg	240µg	240µg
N=2	120µg	165µg	Placebo	240µg	240µg
N=2	120µg	165µg	240µg	240µg	240µg
N=2	Placebo	165µg	240µg	240µg	240µg

^a The participants in Panel A will be randomly assigned.
 A total of 20 participants will participate in Part 2 (Panels A+B+C)

Panel B

Participant (N)	Part 2 ^a Period 1	Part 2 ^a Period 2	Part 2 ^a Period 3
N= 4	300 µg	360 µg	360 µg

Panel C

N = 16 ^b	300 µg	360 µg	360 µg
---------------------	--------	--------	--------

Panel D

N=7 ^c	480 µg	120 µg	120 µg
------------------	--------	--------	--------

^a A total of up to 24 participants will participate in Part 2. (Panels A+B+C+D)

^b The sample size for Panel C may be adjusted depending on the number of participants from Panel A that continue into Part 2 and the start of Panel D. Panel C will not exceed 16 evaluable participants. Participants in Panels B and C will be non-randomly assigned.

^c The sample size for Panel D may be adjusted and will be dependent upon the final number of participants that are enrolled in Panel C. Panel D will not exceed 8 evaluable participants. Participants in Panel D will be non-randomly assigned.

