8.11.6 Study Design/Dosing/Procedures Modifications Permitted Within Protocol Parameters

This is a Phase 1 assessment of MK-5475 in humans, and the PK, pharmacodynamic, and safety profiles of the compound is still being elucidated. This protocol is written with some flexibility to accommodate the inherent dynamic nature of Phase 1 clinical studies. Modifications to the dose, dosing regimen, and/or clinical or laboratory procedures currently outlined may be required to achieve the scientific goals of the study objectives and/or to ensure appropriate safety monitoring of the study participants.

As such, some alterations from the currently outlined dose and/or dosing regimen may be permitted based on newly available data, but the maximum daily dose may not exceed those currently outlined in the protocol.

- Repeat of or decrease in the dose of the study intervention administered in any given period/panel

- Interchange of doses between panels
- Entire period(s) or panel(s) may be omitted
- Adjustment of the dosing interval (eg, divided doses [BID to QD, QD to BID, TID, or vice versa])
- Lengthening of the wash-out period between doses
- Remove a planned PK pause if agreed by Sponsor and investigator if no further increases in total daily dose
- Addition of PK pause
- Instructions to take study intervention with or without food or drink may also be modified based on newly available data
- Modification of the PK/pharmacodynamic sample processing and shipping details based on newly available data
- Changes to the time interval between dosing and the post dose RHC measurements in Part 2
- Changes to the time interval between dosing and the post dose CT scans in Part 2
- Change sequence of RHC and FRI procedure in Periods 2 and 3 of Part 2.
- The PK/pharmacodynamic sampling scheme currently outlined in the protocol may be modified during the study based on newly available PK or pharmacodynamic data (eg, to obtain data closer to the time of peak plasma concentrations). If indicated, these collected samples may also be assayed in an exploratory manner for metabolites and/or additional pharmacodynamic markers.
- Up to additional 50 mL of blood may be drawn for safety, PK, and/or pharmacodynamic analyses. The total blood volume withdrawn from any single participant will not exceed the maximum allowable volume during his/her participation in the entire study (Section 8).

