9.4 Analysis Endpoints

Primary Pharmacodynamic

The primary pharmacodynamic variable in this study is PVR in Part 2, Period 2 (Panel A) and Period 3 (Panels B, C and D).

Primary Safety

The primary safety endpoints in this study include all types of AEs, in addition to laboratory safety assessments, ECGs, PFTs and VS.

Secondary Endpoints for PD

The secondary endpoints in this study include HR and BP.

- Increases from baseline PBV at 1, 3, 8 and 24 hours postdose in Part 2, Period 3 (Panel A) and Period 2 (Panels B, C and D).

Secondary Endpoints for PK

The secondary endpoints in this study include AUC_{0-24hr}, AUC_{0-inf}, C_{max}, C_{24hr}, T_{max} and apparent terminal t_{1/2} after administration of single doses in Panel A Periods 1-3 and Panels B, C and D, Period 1.

Exploratory Endpoints

- Mean pulmonary artery pressure (mPAP), systemic vascular resistance (SVR), cardiac output (CO)/cardiac index (CI) and mixed venous and arterial oxygenation in Part 2, Period 2 (Panel A) and Period 3 (Panels B, C and D).
- PVR/SVR change from baseline at 0.5 through 4.5 hours post-dose Part 2, Period 2 (Panel A) and Period 3 (Panels B, C and D).
- Change from baseline PVR and PBV at 1 and 3 hours postdose in Part 2, Periods 2 and 3.

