Secondary (PK): Separately for each PK parameter (in Panel A, Part 1, Periods 1~3, and Panel B-D, Part 2, Period 1), individual values of AUC_{0-24hr} , $AUC_{0-\infty}$, C_{max} , C_{24} (as appropriate, if <50% C_{24} values are BLOQ) at each dose level will be natural log-transformed and evaluated with a linear mixed effects model containing a fixed effect for treatment and panel, and a random effect for participant. Kenward and Roger's method will be used to calculate the denominator degrees of freedom for the fixed effects. Ninety-five percent confidence intervals for the least squares means for each treatment will be

constructed on the natural log scale and will reference the t-distribution. Exponentiating the least-squares means and lower and upper limits of these confidence intervals will yield estimates for the population geometric means and confidence intervals about the geometric means on the original scale.

Secondary (PBV): Individual PBV will be natural log transformed and analyzed in a linear mixed effects model with fixed effects for dose, time, dose by time interaction and a random effect for subject. The dependent variable is: $\log(\text{PBV at X hour}) - \log(\text{PBV at 0 hour})$. An unstructured covariance matrix for each treatment will be used to allow for unequal variances and different correlations across time and treatment via the REPEATED statement in SAS PROC MIXED (a similar model would be acceptable using R) Kenward and Roger's method will be used to calculate the denominator degrees of freedom for the fixed effects (DDFM=KR). If the model fails to converge, a simpler covariance structure such as compound symmetry may be used. The difference in least squares means on the log scale will be calculated for MK-5475 postdose vs. predose at each time point (1, 3, 8 and 24 hours) at each dose level. These mean differences will be exponentiated to obtain the ratio of geometric means for PBV ($\text{MK_postdose} / \text{MK_predose}$) at each dose level.

Exploratory

The relationship between dose or plasma concentration and pharmacodynamic variables

PVR, pulmonary arterial pressure, cardiac output/cardiac index (CO/CI), systemic vascular resistance, mixed venous oxygen saturation and arterial oxygenation in participants with pulmonary arterial hypertension will be explored graphically. Upon visual inspection, additional model-based analysis might be employed to further explore the pharmacokinetic-pharmacodynamic relationship.

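### The secondary PK model fits fixed panel and fixed dose effects in disconnected blocks, so under the usual LS-mean definition none of the five per-dose LS means is estimable

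*Combined protocol and SAP*

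**What the plan says.** Section 9.6, Secondary (PK), log-transforms AUC0-24, AUC0-∞, Cmax and C24 and fits a "linear mixed effects model containing a fixed effect for treatment and panel, and a random effect for participant". The output is one estimate per dose: "Ninety-five percent confidence intervals for the least squares means for each treatment will be" constructed on the log scale, then exponentiated to geometric means. No weighting over panels is given for the LS means.

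The model covers Panel A in Part 1 and the first period of the other panels. Section 9.4 defines the PK endpoints in the same way: "after administration of single doses in Panel A Periods 1-3 and Panels B, C and D, Period 1".

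The summary in Section 9.1 describes a "linear mixed effects model containing a fixed effect for treatment, and Panel a random effect for participant". That wording does not settle whether panel is fixed or random. Section 9 refers the reader to Sections 9.2 to 9.9 for full detail, so Section 9.6 is taken as the governing text.

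**The concern.** A model with additive dose and panel effects can separate the two only if doses and panels overlap enough to be linked. In these periods they do not: each panel has its own dose or doses, and the one dose given in more than one panel (300 µg, in B and C) connects neither panel to A or D. An LS mean in the usual sense asks what the mean at a dose would be averaged over all four panels. For 480 µg, for example, that needs the effects of Panels A, B and C relative to D, about which the design carries no information.

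Per-dose geometric means with confidence intervals are the stated product of the secondary PK analysis. SAS would report these LS means as non-estimable. Software that drops aliased columns without checking estimability could return numbers that depend on column order and reference level. Either way the model would have to be re-chosen after the data are in and listed as a deviation under Section 9.2.

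**Working it through.** The plan states no figure to reproduce here, so the check is of the design itself.

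**Inputs.** Doses by panel in the periods the model uses (Table 1, Section 4.2, Table 3):

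| Panel | 120 | 165 | 240 | 300 | 480 |
|---|---|---|---|---|---|
| A (Part 1, Periods 1–3) | ✓ | ✓ | ✓ | | |
| B (Part 2, Period 1) | | | | ✓ | |
| C (Part 2, Period 1) | | | | ✓ | |
| D (Part 2, Period 1) | | | | | ✓ |

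Six cells are occupied. They form three blocks: {A; 120, 165, 240}, {B, C; 300} and {D; 480}.

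**Rank.** For an additive two-factor model, rank = doses + panels − blocks = 5 + 4 − 3 = 6. A connected layout would give 5 + 4 − 1 = 8. A numerical check on the 10-column matrix (intercept, 5 doses, 4 panels) also gives 6.

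**Estimability of the LS means.** Within any one block, add a constant c to every dose effect and subtract c from every panel effect. All fitted values stay the same, so an estimable quantity must not move. With equal panel weights of 1/4:

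- 120, 165 or 240 µg, shifting the first block: c − c/4 = 0.75c.
- 300 µg, shifting the second block: c − 2c/4 = 0.5c.
- 480 µg, shifting the third block: c − c/4 = 0.75c.

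All five move, so 0 of 5 are estimable. With overall observed-margin weights the shift is c × (1 − the total weight of the panels in that block). This is zero only if one block holds all the data, so the count is again 0 of 5.

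In simulated data, two solutions with identical fitted values gave LS means at 120 µg of 0.366 and 0.115, and at 480 µg of −0.914 and −0.420.

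**Dose differences.** Only differences inside a block survive: 120–165, 120–240 and 165–240, which is 3 of 10.

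**Cell means.** All 6 of 6 are estimable.

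**Does anything in the plan rescue the model?**

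- *Sample size.* The rank depends on which cells are occupied, not on how many participants are in them. The random participant effect does not change it either.
- *Dose interchange.* Section 8.11.6 permits "Interchange of doses between panels". There are 20 − 6 = 14 unoccupied cells. Of these, 7 would join the first and second blocks, 4 the first and third, and 3 the second and third. One extra cell joins only two blocks, so none of the 14 is enough alone. With two extra cells, 7×4 + 7×3 + 4×3 = 61 of the 91 possible pairs connect everything, but none is planned.
- *Later periods.* Adding Periods 2 and 3 of Panels B to D (360 µg in B and C, 120 µg in D) links A with D but leaves B and C apart: two blocks, and 0 of 6 dose means estimable.

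**With panel removed.** Rank is 5 for 5 doses; all 5 means and all 10 differences are estimable.

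**With panel random.** The means are estimable, but the panel variance rests on rank[dose, panel] − rank[dose] = 6 − 5 = 1 degree of freedom, from B against C at 300 µg.

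**The case against.** The strongest reply is that the result depends on how the LS means are averaged, which the plan leaves open. If each dose is averaged only over the panels that received it, the shifts above cancel and all five means are estimable with panel kept. That is correct, and it would be an acceptable repair. But it is not the usual meaning of an LS mean, and Section 9.6 does not ask for it.

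The wording could also be read in other ways. A fixed effect for treatment and panel, in the singular, might mean one combined factor. All six cell means would then be estimable, but there would be two results at 300 µg instead of the one per treatment that is promised. Section 9.1 might be read as a random panel effect, but Section 9.6 places panel with treatment under the fixed effects.

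There is also a case for keeping panel. Section 2.2.3 reports moderate to high variability in exposure, and geometric mean AUC0-24 at 360 µg ran from 1.21 to 4.28 nM·hr, a ratio of 4.28/1.21 = 3.54. Those values lie outside this model's data and mix panel with period. They do support showing 300 µg by panel as well as pooled.

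Finally, the analysis is secondary and tests no hypothesis, and in SAS the failure would be obvious at the first run. This limits the consequences but does not make the stated rule deliver its stated output.

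**Conclusion.** The concern holds. As Section 9.6 is written, and with LS means averaged over panels in either of the usual ways, none of the five promised per-dose means can be estimated and only three of ten dose differences can. This rests on three things: panel is fixed and additive, as Section 9.6 states; the data are the periods named there; and doses follow Table 1 without unplanned interchange. It does not depend on the number of participants.

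The practical reach is limited. No data are lost, and every cell mean is available. Four of the five doses come from a single panel, so the only real choice is how to combine B and C at 300 µg. It is a specification error that should be corrected before analysis, not a threat to the trial.

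**What to change.** In Sections 9.1 and 9.6, specify fixed treatment (five dose levels) and random participant, with no panel term, and make the two sections agree. State that 300 µg is pooled over Panels B and C and that its values are also summarised by panel. If by-panel results are wanted as the main output, say instead that the six panel-by-dose cell means will be reported. If panel is to stay in the model, define each dose's LS mean over the panels that received it and give the weights. A random panel effect is the weaker choice because of its single degree of freedom.

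The cost is a wording change, with no new data. Differences between panels remain mixed with dose, but the design cannot separate them under any model: Table 3 states that "Participants in Panels B and C will be non-randomly assigned" and "Participants in Panel D will be non-randomly assigned". The one same-dose comparison in the model's data is 300 µg, where Section 2.2.3 reports that geometric mean AUC0-24 at this "dose level ranged from 2.08 to 2.35 nM*hr across study panels", a ratio of 2.35/2.08 = 1.13. That is mild reassurance for pooling B and C and says nothing about Panels A or D.
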